7.6.1. Safety Criteria for Dose Adjustment or Stopping Doses

For the purposes of determining continued dosing within a cohort or dose escalation to a subsequent planned cohort, stopping rules are based on the emergence of DLTs. Nonextreme and extreme DLTs will be considered related AEs/serious adverse events (SAEs) and will be recorded/reported as such.

Dosing of study drug and study enrollment will be halted (temporarily or permanently) as follows:

- Occurrence of any extreme DLT (dosing and enrollment to be halted immediately; PI, research monitor, PVG physician, and DSMB will review and make a recommendation to the sponsor, which will determine if dosing and enrollment may continue);
- Emergence of a specified number (see [Table 6](#)) of nonextreme DLTs among subjects in a particular dosage group (DSMB will review to determine whether dosing and enrollment may continue);
- Occurrence of an SAE not already designated as an extreme or nonextreme DLT, determined to be possibly, probably, or definitely related to the investigational product; dosing and enrollment to be halted immediately until the DSMB has completed a safety review; and

- Sponsor, DSMB, or PI's clinical judgment warrants stopping based on ongoing review of the safety profile.

The maximum tolerated dose will be the highest dose at which none of the following has been observed:

- An extreme DLT in any one subject;
- A nonextreme DLT in 2 of the first 4 subjects or in 3 subjects at any time; and
- Any SAE, not already categorized as a DLT that is considered to be possibly related, probably related, or definitely related to the study drug.

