If an SAE occurs at any time that is not already designated as an extreme or nonextreme DLT, unless it is reported as **unrelated** to the study drug, enrollment and dosing will also be halted pending review by the DSMB. While the presence of any specific AE may not necessarily halt enrollment, careful reporting of these events is necessary. After thorough review by the DSMB and consultation with the investigators, a decision will be made by the sponsor whether to proceed with the dosing escalation.

If any of the above events occurs, administration of investigational product will be discontinued until a thorough review of the events is undertaken by the investigators, local Institutional Review Board (IRB) and/or [REDACTED]

[REDACTED], research monitor, and/or sponsor's safety office [REDACTED]. The study may be resumed with the concurrence of the research monitor, PVG physician, sponsor's representative, PI, and the FDA.

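### A related serious event that is also a listed nonextreme DLT stops the trial under Protocol 7.6, yet as a single event in subjects 5 to 8 it meets no halting row in Table 6

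*Protocol*

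**What the plan says.** The protocol holds two sets of halting text that reach the same event.

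- **Any-DLT sentence.** Protocol 7.6, repeated in Section 11, stops dosing and enrollment at once for a DLT of any kind, pending review. It does not separate extreme from nonextreme.
- **Tiered triggers.** Protocol 7.6.1 opens with "Dosing of study drug and study enrollment will be halted (temporarily or permanently) as follows" and then lists triggers. The SAE trigger is confined to "Occurrence of an SAE not already designated as an extreme or nonextreme DLT" that is judged at least possibly related. Nonextreme DLTs are sent to the counts in Table 6.
- **The exemption repeated.** Protocol 7.6.1.3 limits the SAE halt in the same way before Table 6, in the table's SAE row, and again after it: "If an SAE occurs at any time that is not already designated as an extreme or nonextreme DLT". SAP Table 3 has the same row.
- **The counts.** Table 6 halts dosing at 1 nonextreme DLT in the first 4 subjects or 2 in the first 8. It halts dosing and enrollment at 2 in the first 4 or 3 in total.
- **Backstops.** The last paragraph of 7.6.1.3 says "If any of the above events occurs, administration of investigational product will be discontinued until a thorough review of the events is undertaken". The last trigger in 7.6.1 lets the sponsor, DSMB or PI stop when "clinical judgment warrants stopping based on ongoing review of the safety profile".
- **Recording.** Protocol 7.6.1 also says "Nonextreme and extreme DLTs will be considered related AEs/serious adverse events (SAEs", so the plan foresees that one event can carry both labels.

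**The concern.** The overlap is easy to foresee. Symptomatic bronchospasm is a nonextreme DLT (Protocol 7.6.1.2), and a narrower form, allergic and needing intensive treatment, is an SAE example in 11.2.2. Delirium that responds to physostigmine is a nonextreme DLT (7.6.1.2 and 9.2.1), and an investigator could judge it serious as an important medical event needing intervention.

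A halting rule in healthy volunteers should give one answer to the question of whether one such event stops the cohort. Here one party could cite 7.6 and another Table 6. Section 11 says the DSMB charter contains the stopping and continuation criteria. The charter is not among the documents, so which rule the DSMB would apply cannot be checked.

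**Working it through.** Neither document gives a figure for this point, so the check is to follow one event through each rule. Take one possibly, probably or definitely related event that meets both 11.2.2 and a nonextreme-DLT criterion, with no other event in the cohort.

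| Text | Event in subjects 1–4 | Event in subjects 5–8 |
|---|---|---|
| Protocol 7.6 and Section 11, any DLT | Dosing and enrollment stop | Dosing and enrollment stop |
| Protocol 7.6.1 SAE trigger, 7.6.1.3, Table 6 SAE row, SAP Table 3 SAE row | Exempt | Exempt |
| Table 6 and SAP Table 3, nonextreme rows | Dosing halted; the 7.6.1 lead-in adds enrollment | No row met |
| Guideline text under Table 6 | DSMB to consider enlarging the cohort from 8 to 12 | The same |
| Last paragraph of 7.6.1.3 | Product stopped | Product stopped, if its reference to the events above is read to include a single nonextreme DLT; enrollment not mentioned |
| SAP 3.3.1 narrative | Dosing and enrollment stop; exemption not stated | The same |

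**Where the rules part.** In subjects 1–4 they nearly agree. Table 6 mentions dosing only, but the 7.6.1 lead-in covers enrollment, and Protocol 9.1.1.1 treats a subject as enrolled when dosed. In subjects 5–8 the any-DLT sentence requires a stop and the count table requires nothing.

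**How many active subjects sit there.** Under SAP 3.6 the first block of 2 has 1 active subject and the next block of 6 has 5.

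- Subjects 3 and 4 include at most one placebo, so they contribute 1 or 2 active subjects.
- The first 4 subjects therefore hold 1 + 1 = 2 or 1 + 2 = 3 active.
- Subjects 5–8 hold the rest: 6 − 2 = 4 or 6 − 3 = 3 active.

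So 3 or 4 of the 6 active subjects are in the positions where the texts disagree.

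**Whether another section settles it.** Protocol 12.3 refers halting criteria to Section 7. Both 7.6 and Table 6 are in Section 7, so the reference does not choose between them. SAP Section 1 lets the SAP override the protocol for analyses, which does not reach dosing rules.

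**The case against.** The strongest reply is that this is mostly loose drafting with little practical effect. Much of that stands.

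- **The SAP is not a rival rule.** A reader might infer a third rule from SAP 3.3.1 and 6.4, whose narrative halts for a related SAE without stating the exemption. The documents do not support that. SAP 6.7.1 says the halting criteria are those in SAP Table 3, which carries the exemption, and Table 8 inside SAP 6.4 carries it too. The narrative is imprecise wording and a secondary matter.
- **Dosing would probably not continue unreviewed.** A reader might infer that the cohort would carry on after a serious event in subjects 5–8. The closing paragraph of 7.6.1.3, the judgment stop and the any-DLT sentence itself all point to a pause. Resumption is also demanding: "The study may be resumed with the concurrence of the research monitor, PVG physician", together with the sponsor's representative, the PI and the FDA.
- **The any-DLT mismatch is wider than serious events.** It affects every single nonextreme DLT, serious or not. That is correct, and it is why the fix has to cover both.

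The conflict inside Section 7 survives. The closing paragraph needs an interpretation to reach a lone nonextreme DLT, and the judgment stop is discretionary. Neither says which of 7.6 and Table 6 governs.

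**Conclusion.** The point holds as an internal contradiction in Protocol Section 7. For a related event that is both serious and a listed nonextreme DLT, 7.6 and Section 11 require a halt at one subject. The operative tables take the event out of the SAE row and, in subjects 5–8, leave it with no row at all. It is worth correcting before dosing, but the practical gap is limited by the backstops above. No frequency or error rate is claimed, because that would need an event risk that the documents do not give. The conclusion assumes an unexpanded cohort under the SAP 3.6 blocks and that the DSMB charter does not already resolve the matter.

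A reader might go further and infer that the maximum tolerated dose (MTD) definition is also wrong, because its third criterion covers only "Any SAE, not already categorized as a DLT that is considered to be possibly related, probably related, or definitely related to the study drug". The documents do not support that. The exemption is express, such events still count under the second criterion, and how many should bar a dose is a risk-tolerance choice for the sponsor. The MTD is also not an objective or endpoint in Protocol 6.1 and 7.1 or SAP Section 2.

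**What to change.** 1. In Protocol 7.6.1, 7.6.1.3, a note to Table 6, and SAP 3.3.1 and Table 3, state: when a possibly, probably or definitely related event meets both a nonextreme-DLT criterion (7.6.1.2) and the SAE definition (11.2.2), dosing and enrollment halt at one subject pending DSMB review and sponsor decision.
2. Change the recording sentence in 7.6.1 so that DLTs are recorded as related AEs, and as SAEs only if they meet 11.2.2. Listed events that are not serious then stay in the counted tier.
3. In the same edit, reconcile the any-DLT sentence in 7.6 and Section 11 with the Table 6 counts for listed events that are not serious. The sponsor decides which of the two governs.
4. Keep the existing conditions for resuming, including FDA concurrence, and leave the MTD definition as it is.

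The cost is wording in both documents, with no added subjects or procedures. The downside is that one serious listed event pauses the cohort, which 7.6 and Section 11 already require.

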5.4. Route of Administration, Dosage Regimen, Treatment Period, and Justification

Up to 240 subjects will be consented and screened for participation in the study.

This is a double-blinded, randomized, placebo-controlled, in-clinic, Phase 1, single-dose, IM, sequential dose-escalation study in healthy adults aged 18-55. Healthy volunteers will be assigned to 1 of 5 cohorts of Scopolamine HBT dosage groups: 0.005, 0.007, 0.011, 0.014, or 0.021 mg/kg, or receive the placebo, administered by IM injection to the anterior thigh. In each cohort, 6 to 9 subjects will receive active drug and 2 to 3 subjects will receive placebo. Each cohort will have at least 3 male and 3 female subjects enrolled among the first 8 subjects in the dosing group to ensure that at least 1 male subject and 1 female subject in each dosing group receive active drug. If nonextreme dose-limiting toxicities (DLTs) are observed in any of the cohorts, 4 additional subjects, 3 active and 1 placebo, may be added to each cohort.

On the first day of dosing for each cohort, 2 subjects will be dosed (1 active and 1 placebo). Upon review of the adverse event (AE) data for both subjects at 24 hours post dose (\pm 1 hour), the principal investigator (PI) and the medical monitor will determine if it is safe to proceed with dosing the remaining 6 of the first 8 subjects.

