7.6. Dose-adjustment Criteria

New subjects will not be enrolled into the next higher dosage group until at least 8 subjects in the previous cohort have completed the Day 8 follow-up visit without the occurrence of DLTs, and the DSMB has made a recommendation to the sponsor regarding dose escalation. The sponsor must approve the dose escalation and notify the investigator(s) before any new subjects can be enrolled. The occurrence of any DLT(s) would result in the immediate discontinuation of dosing and study enrollment, pending a review of study data by the PI, research monitor, PVG physician, the DSMB, and the sponsor.

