7.6.3. Study Termination Criteria

The PI, research monitor, sponsor's representative, the local IRB, and/or the [REDACTED], DSMB, or the FDA may stop or suspend the use of this product at any time.

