12.1.2. Safety Analyses

Safety analysis will include data collected from the safety analysis set. DLT and AE data will be coded using the current MedDRA version at the time of study setup, listed individually (including intervention and outcome), and summarized by system organ class and preferred terms within a body system for each treatment group. Data will be summarized by both event (counting each event regardless of subject) and by subject (counting only one event within each system organ class or preferred term). Serious and/or unexpected AEs will also be discussed on a case-by-case basis.

Changes in pulse rate, systolic and diastolic blood pressure, weight, and respiratory rate will be summarized (mean, median, minimum, maximum, standard deviation) by dose level and time point. Clinical laboratory assessment results will be presented.

Upper bounds of 80% confidence intervals of the true probability of events (extreme DLTs, non-extreme DLTs, and severe AEs) will be estimated from the number of events in each cohort using the Pearson-Clopper method.

Descriptive statistics of BPRS, C-SSRS, DSST, RASS (if conducted), and injection site VAS scores (mean, median, standard deviation, minimum, and maximum) will be presented for each dose level and time point.

Changes in the BPRS score (6 hours, 48 hours, and 8 days) from baseline will be compared between placebo and active dose levels using ANOVA models for each time point. The null hypothesis of no difference between placebo and the active dose will be tested for each dose level using a one-sided alternative hypothesis of higher increases among the participants receiving the active drug than among the placebo group.

Participants have C-SSRS scores of zero at baseline. The proportion of individuals having any increase in their C-SSRS score from zero will be compared for each drug dosage level to the placebo group using Fisher's exact test.

The DSST will be conducted at screening, Day -1, Day 3, and Day 8. Changes from baseline (Day -1) will be compared between placebo and active dose levels using ANOVA models for each time point. Placebo control will help to exclude any remaining practice effects or changes

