12.2. Planned Enrollment and Reason for Sample Size

The sample size calculation of 40-60 healthy subjects has been chosen to provide adequate numbers of subjects for characterization of the safety and tolerability of Scopolamine HBT administered in 1 to 5 dose-escalating cohorts in normal, healthy volunteers as well as a placebo group. No formal statistical sample size computation was performed; however, the 6 to 9 active subject and 2 to 3 control subject design is commonly employed in Phase 1 clinical trials because it provides adequate power to detect non-rare events (true probability, $P > 0.20-0.25$) events within each cohort. Enrollment may be stopped at any dosing level if stopping criteria are met; therefore, the total sample size may be substantially smaller than 40-60.

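### The MTD definition in Protocol 7.6.1 has no 'not reached' outcome and ignores permanent safety-judgment stops, so it can mislabel the last dose opened

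*Protocol*

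**What the plan says.** Protocol 7.6.1 introduces its halting rules with "Dosing of study drug and study enrollment will be halted (temporarily or permanently) as follows" and gives four grounds:

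- any extreme DLT;
- a set number of nonextreme DLTs (Table 6);
- a related SAE not already classed as a DLT;
- a situation in which sponsor, DSMB or PI "clinical judgment warrants stopping based on ongoing review of the safety profile".

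The MTD sentence comes directly after this list: "The maximum tolerated dose will be the highest dose at which none of the following has been observed". Its three items are an extreme DLT in one subject, a nonextreme DLT in 2 of the first 4 subjects or in 3 overall, and a related SAE outside the DLT categories. The fourth halting ground is not carried over. The sentence does not ask for a completed cohort or for any sign of a limit at a higher dose, and it gives no outcome for a trial that finds no limit.

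Other relevant text:

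- Protocol 7.6: the next dose opens only when "at least 8 subjects in the previous cohort have completed the Day 8 follow-up visit".
- Protocol 5.4 and 7.2: each cohort starts with one active and one placebo subject. The PI and medical monitor then decide whether to continue.
- Protocol 7.6.3: several named bodies "may stop or suspend the use of this product at any time".
- Protocol 12.2: "Enrollment may be stopped at any dosing level if stopping criteria are met".
- Protocol 12.1.2 and SAP 6.4: the per-dose safety summary is "Upper bounds of 80% confidence intervals of the true probability of events". The SAP does not mention an MTD.

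**The concern.** An MTD is normally read as a statement that a limit was located, or at least that the dose was adequately tested and accepted. This definition secures neither. A trial that runs all five cohorts without meeting a criterion would report 0.021 mg/kg, simply the last dose planned, as the MTD. A trial whose last cohort was abandoned on safety judgment would report the abandoned dose as tolerated.

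Tolerability is part of a primary objective (Protocol 6.1), and SAP section 1 says that future dosing will rest partly on this study's safety data. A wrong label in the report could therefore travel further than the tables behind it.

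**Working it through.** **Step 1: apply the literal rule to trial paths.** The doses are 0.005, 0.007, 0.011, 0.014 and 0.021 mg/kg (Protocol Table 7).

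| Path | Literal MTD | What happened |
|---|---|---|
| A. All five cohorts complete, no criterion met | 0.021 | No limit found |
| B. 0.014 permanently stopped on safety judgment, no listed event | 0.014 | Dose abandoned for safety |
| C. Criterion met at 0.014, trial ends there, lower doses clean | 0.011 | Rule works as intended |

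**Step 2: how far path B reaches.** The 8-subject Day 8 condition in Protocol 7.6 covers every dose below the last one opened. A thin or abandoned cohort can therefore only be the final one. Within that cohort, the smallest number of active subjects is one, because the first pair is one active and one placebo (SAP 3.6 fixes this as a block of 2).

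**Step 3: is path B plausible?** Protocol 5.2.4 describes an earlier study in which 0.014 mg/kg IM left healthy volunteers confused, uncoordinated and physically incapacitated. Under 7.6.1.1 and 7.6.1.2, symptoms such as delirium or hallucinations count as DLTs only if they need medication or if BPRS thresholds are met at 48 hours. Effects could worry the PI or DSMB enough to stop without meeting a listed criterion. The documents give no probability for this, and none is assumed here.

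**Step 4: how little evidence could support the label.** The upper limit of an 80% Clopper-Pearson interval (10% in the upper tail) with zero events in n subjects is 1 − 0.10^(1/n).

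- The plan's own figure, n = 6: 1 − 0.10^(1/6) = 0.319. This matches the 0.32 in SAP 6.4 and Table 8.
- One active subject, n = 1: 1 − 0.10 = 0.90.

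SAP 6.6.3 keeps any cohort with at least one dosed participant in the analysis if the study is terminated. A bound of 0.90 could then be reported beside an MTD label for the same dose.

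**Step 5: look for a correction elsewhere.** Neither the rest of the protocol nor the SAP redefines the MTD or supplies a 'not reached' outcome.

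**The case against.** The strongest reply is that nothing in the trial uses the label. The term is defined once and is absent from the objectives, the endpoints (Protocol 7.1, Table 12) and the SAP. Tolerability is characterised through AE tables and per-dose upper bounds, which are unaffected. This stands, and it limits the point to reporting.

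Second, some trials call the top tolerated dose the MTD by convention, and the protocol is free to define its own term. That is fair as usage, but the text does not tell the reader which meaning applies, and a 'not reached' outcome would settle it.

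Third, path B is narrow. The DLT lists are broad, each cohort is specified as 6 to 9 active subjects, and a sensible author would not call a stopped dose tolerated. The path is narrow, but the protocol provides for it in the fourth halting ground and in 7.6.3, and the written rule still gives the wrong answer.

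Fourth, the DSMB charter, which Protocol section 11 says holds stopping and continuation criteria, is not available here. It may say more, so the claim that nothing corrects the definition covers the protocol and SAP only.

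A reader might also infer that the MTD must lie below the lowest dose that met a criterion. Suppose a criterion is met at 0.011 mg/kg, review clears the trial to continue, and 0.014 and 0.021 are clean. The literal rule gives 0.021, and a below-the-lowest-failure rule would give 0.007. The documents do not require the second reading: 7.6.1.3 and Table 6 let the sponsor continue after review, so a cleared halt is not a failed dose. By the same reasoning, a cleared halt at 0.005 mg/kg would not mean that no tolerated dose exists.

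**Conclusion.** The point holds as a small defect in a reporting rule. Two outcomes that the protocol itself allows would be mislabelled: no limit found (0.021 mg/kg called the MTD), and a final cohort permanently stopped on safety judgment (that dose called the MTD, possibly on 0/1 with an upper bound of 0.90, against 0.32 for 0/6).

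A reader might infer a weakness in subject protection. The documents do not support that, because halting and escalation run on the four grounds, Table 6, DSMB review and sponsor approval, and none of these refers to the MTD. A reader might also take the wider bounds in SAP Table 8, such as 0.51 for 1/6 or 0.67 for 2/6, as measures of this flaw. They are not: they reflect cohort size and the nonextreme-DLT threshold, and would be the same under any label.

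The conclusion assumes that the definition is applied as written and that the unavailable DSMB charter does not override it. It merits a wording change and no change to the design.

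**What to change.** Keep the three criteria and add to Protocol 7.6.1:

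*A dose qualifies as the MTD only if its planned cohort (at least 8 subjects) completed Day 8 and dosing at that dose was not permanently stopped on sponsor, DSMB or PI safety judgment. If no dose met a criterion or was permanently stopped for safety, report 'MTD not reached; highest dose tested' with that dose's SAP 6.4 upper bound.*

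Under this text, path A becomes 'MTD not reached; highest dose tested', 0.021 mg/kg. Path B becomes 0.011 mg/kg, provided that dose met no criterion; its cohort must already have completed Day 8 for 0.014 to open. A halt that was reviewed and cleared is treated as the protocol treats it now, so a cleared criterion at a lower dose does not cap the MTD.

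The cost is two sentences, a slightly less favourable label in some outcomes, and the need to document why any permanent stop was made. Halting rules, escalation and SAP analyses are unchanged.
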